## 6.11.2 Sensitivity Analysis of the First Co-Primary Endpoint

Sensitivity analysis may be carried out using the Cochran-Mantel-Haenszel (CMH) test stratified by the randomization stratification factor (baseline TSS [ $<28$  vs.  $\geq 28$ ]) to assess robustness of the Fisher's exact test results.

A sample SAS code for the pairwise comparison is as follows.

```
* COMPUTES CMH P-VALUE AND NEWCOMBE COMMON RISK DIFFERENCE ;
ods output CMH=PVAL(where=(alhypothesis='Row Mean Scores Differ')) ;
CommonPdiff=DIFF;
proc freq data=ADEF ;
  tables TSS_STRAT*TRTP*RESP / cmh commonriskdiff
  (cl=NEWCOMBE) ;
run ;
```

The rationale for specifying the Fisher's exact test as the primary analysis as opposed to specifying the CMH is because when a stratum has 100% response for 1 treatment group and 0% response for another treatment group, the CMH test may lose efficiency or not be computable. This is evident from the Phase 2 study outcome.

## 6.11.3 Subgroup Analysis of the First Co-primary Endpoint

Analysis comparing AK002 and placebo will use the Fisher's exact test for each of the subgroups defined in Section 5.9.

## 6.11.4 Analysis of the Second Co-Primary Endpoint

The second co-primary endpoint will be analyzed using mixed model for repeat measures (MMRM) with treatment, week, treatment-by-week interaction, and baseline TSS-by-week interaction as fixed factors, gender, and baseline TSS (continuous) as covariates, and study site (with pooling by geographic location) as random effect. If the model does not converge with pooled sites as a random effect, it will be simplified with pooled site as a fixed effect.

The weekly TSS score is calculated as the average of the daily TSS scores. Weekly TSS will be set to missing if  $>3$  daily TSS are missing. Baseline TSS score will be the average of the last 2 weeks of daily TSS collected prior to the first infusion. The model variance-covariance matrix will be unstructured. However, if computation does not converge, the matrix will take the form of Toeplitz, autoregressive, or compound symmetry, whichever converges first. A sample of the SAS code for MMRM analysis is provided as below:

```

proc mixed data=tss method=reml;
  class TRTMT USUBJID AVISITN ANALYSIS_CENTER GENDER;
  model CHG= B_TSS TRTMT AVISITN ANALYSIS_CENTER GENDER
  TRTMT*AVISITN B_TTS*AVISITN / DDFM=KR;
  REPEATED AVISITN / SUBJECT=USUBJID (TRTMT) TYPE=UN;
  RANDOM ANALYSIS_CENTER;
  LSMEANS TRTMT*AVISITN / PDIFF CL;
ESTIMATE 'PBO VS. AK002 at WEEKS 23-24' TRTMT -1 1
  TRTMT*AVISITN 0 0 0 0 0 0 0 0 0 0 -1
  0 0 0 0 0 0 0 0 0 0 0 1 / CL;
RUN;

```

Where TRTMT = planned treatment group in numeric (1 = placebo, 2 = AK002); AVISITN = time point (i.e., Weeks 1-2, Weeks 3-4, ..., Weeks 23-24).

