second co-primary endpoint is confounded by the influence of background variables, then the second co-primary analysis will be conducted adjusting for the effects of the background variables. Possible confounding factors may include age, presence of esophageal inflammation, history of IBS, and presence of diarrhea at baseline.

Two sensitivity analyses are planned. The first is a pattern-mixture model, where it will be assumed that AK002 patients who experience an ICE will have a trajectory comparable to placebo post-ICE. This analysis will therefore provide a stress test of the missing at random (MAR) assumption of the MMRM employed in the principal analysis and will provide a conservative estimate of the treatment effect. The pattern-mixture model will be implemented using multiple imputations, and the inference of this sensitivity analysis will be based on the combined estimates using the standard multiple imputation technique. The imputed data sets will be analyzed with the same MMRM model utilized in the primary analysis and then summarized using PROC MIANALZE. The other is to analyze the average of Week 23 through Week 24 using ANCOVA with treatment and study site as factors, gender and baseline TSS (continuous) as covariates. Missing Week 23 through Week 24 weekly TSS will be imputed prior to ANCOVA using SAS PROC MI under the MAR assumption.

Detailed specifications for the missing data imputation will be provided in the SAP.

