#### **3.2.3 Methods of Assigning Subjects to Treatment Group**

Approximately 80 subjects with active EoD (without EG) will be stratified by baseline TSS. Subject will be randomized 1:1 to receive 1 of 2 dose regimens using stratified randomized blocks in a double-blind manner.

- 6 doses of AK002 at 3 mg/kg administered every 4 weeks
- 6 doses of placebo

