### 3.5 Determination of Sample Size

A total of approximately 80 subjects will be enrolled.

**First Co-Primary Endpoint:** A sample size of 40 subjects per treatment group will have >90% power to demonstrate a greater proportion of histologic responders at Week 24 in AK002 subjects compared to placebo subjects, assuming the proportions of histologic responders are 0.6 and 0.1 in AK002 and placebo groups, respectively.

**Second Co-Primary Endpoint:** A sample size of approximately 40 patients per treatment group will provide 80% power to detect a statistically significant difference of 7.4 points between AK002 and placebo in the mean reduction from Baseline in TSS at Weeks 23-24, assuming a common standard deviation of 12.5 points (AK002-003 data on file).

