Subsequently, a supplementary analysis of data from a recent study, AK002-016, focused on identification of baseline characteristics which correlate with degree of change in TSS6 at Weeks 23-24. This examination identified eight variables (age, gender, duodenal eosinophil counts, diarrhea frequency, history of IBS, abdominal pain, esophageal eosinophils per hpf  $> 6$ , and history of IBS in combination with diarrhea intensity  $\geq 3$ ) that most influenced the degree of change of the TSS endpoint. Two of the variables (esophageal eosinophils per hpf  $> 6$ , and history of IBS in combination with diarrhea intensity  $\geq 3$ ) potentially reflect other disease states (IBS, GERD or even active EoE) that could potentially impact multiple symptom components of TSS6. To ensure these two variables do not compromise the capacity to detect the treatment effect with symptoms of EoD as measured by the TSS questionnaire, the primary comparison of AK002 vs placebo will be conducted on the Evaluable population defined as subjects who do not exhibit any of the following conditions at baseline:

1.  $> 6$  eosinophils per hpf in at least one esophageal site.
2. Documented history of irritable bowel syndrome and baseline diarrhea intensity  $\geq 3$ .

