## 5.8 Multiple Comparisons/Multiplicity Adjustment

To control for the family-wise type-I error rate, the following testing procedures will be implemented:

Test each co-primary efficacy endpoint at 2-sided  $\alpha=0.05$  level.

- If  $p \leq 0.05$  for both co-primary endpoints, then reject the null hypothesis that AK002 is no different from placebo and accept the alternative hypothesis that AK002 is superior to placebo in reducing tissue eosinophil count and TSS score.
- If  $p \leq 0.05$  for both co-primary endpoints, the hypothesis tests for the secondary endpoints will proceed in the prespecified order.
- If  $p > 0.05$  for either co-primary endpoint, the null hypothesis is accepted. No hypothesis test will be performed for the secondary endpoints.
- The issue of multiplicity of secondary endpoints will be handled by statistical testing of these outcomes in a hierarchical fashion. The order of secondary endpoints is described in Section 2.2. If at any point during the analysis of the secondary endpoints, the statistical test is not significant at 2-sided  $\alpha=0.05$  level, the hypothesis testing procedure will stop. AK002 will be deemed superior to placebo for all endpoints prior to the stop.

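### The primary TSS model has no term for four baseline variables the sponsor found influential, and the protocol's undefined conditional-adjustment clause is dropped by the SAP without being withdrawn

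*SAP*

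**What the plan says.** **The influential variables.** SAP 4.2.1 (and Protocol 4.5.1) reports a supplementary analysis of AK002-016 that found eight baseline variables "that most influenced the degree of change of the TSS endpoint": age, gender, duodenal eosinophil count, diarrhea frequency, IBS history, abdominal pain, more than 6 esophageal eosinophils/hpf, and IBS history combined with diarrhea intensity of at least 3. The last two become exclusions from the Evaluable population, which is the primary analysis population (SAP 6.1.5).

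**The primary model.** SAP 6.11.4 specifies an MMRM with treatment, week, treatment-by-week, baseline TSS-by-week, pooled site, and "gender, and baseline TSS (continuous) as covariates". The sample code agrees.

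**The conditional clause.** Protocol 15.6.1 and the synopsis say that if it is evident that the "second co-primary endpoint is confounded by the influence of background variables", the co-primary analysis will be adjusted for them. Age, esophageal inflammation, IBS history and diarrhea are given as possible examples.

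**Which document governs.** SAP section 1 says the SAP supersedes the protocol's statistical methods. The opening of Protocol section 15 says the same and adds that the SAP will detail any modifications. The SAP neither repeats the clause nor lists it as removed. SAP 5.1 lets alternative methods be considered before database lock if assumptions fail, with the reason recorded in an SAP amendment or in the CSR. SAP 5.6 releases the randomization code only after lock.

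**The concern.** There are two linked gaps.

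First, the sponsor identified predictors of TSS change and then gave four of them no term in the model. The Evaluable restriction does not cover them. It removes IBS history only when combined with diarrhea intensity of at least 3, so patients with IBS history and little diarrhea remain, as do patients with diarrhea and no IBS history. Baseline eosinophil count is already in the TSS imputation models (SAP 5.4.2 and 6.11.5), and no reason is given for leaving it out of the primary model.

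Second, the protocol clause defines no trigger and no final list, and does not say whether the decision is blinded. A reader of both documents cannot tell whether an adjusted result would be primary, supplementary or not produced.

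TSS is the co-primary with little room. Both co-primaries must succeed, and TSS did not separate from placebo in AK002-016 (p=0.343, Protocol Table 1).

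**Working it through.** **1. Where each of the eight variables goes**

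| Variable | Handling |
|---|---|
| Gender | Model term |
| >6 esophageal eosinophils/hpf | Evaluable restriction |
| IBS history with diarrhea intensity ≥3 | Evaluable restriction |
| Abdominal pain | One of six items in baseline TSS, so partly carried |
| Age | No term |
| Duodenal eosinophil count | No term (in the imputation models only) |
| Diarrhea frequency | No term |
| IBS history alone | No term |

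**2. The plan's own power figure**

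Inputs: SAP 3.5, "A sample size of approximately 40 patients per treatment group", which "will provide 80% power to detect a statistically significant difference of 7.4 points between AK002 and placebo", "assuming a common standard deviation of 12.5 points"; SAP 3.2.3, "Subject will be randomized 1:1 to receive 1 of 2 dose regimens"; SAP 5.8, "Test each co-primary efficacy endpoint at 2-sided" alpha of 0.05.

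- SE of the difference = 12.5 × √(2/40) = 2.795.
- Noncentrality = 7.4 / 2.795 = 2.648.
- Normal power = Φ(2.648 − 1.960) = 75.4%. With the noncentral t on 78 df it is 74.4%.

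The stated 80% is not reproduced. That is a separate sample-size matter. Here 74.4% is the unadjusted reference.

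**3. Power after adding k covariates**

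The documents give no R2, so it is assumed. R2 is the share of the 12.5-point variance that the added covariates explain. The calculation uses a single-time-point linear model, not the full MMRM.

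- SE = 12.5 × √(1 − R2) × √[(2/n) × F], with F = (2n − 3)/(2n − 3 − k) for the expected loss from chance imbalance.
- df = 2n − 2 − k.
- n = 40, k = 4: F = 77/73 = 1.055, df = 74.
- Example at R2 = 10%: SE = 11.859 × √(0.05 × 1.055) = 2.723; noncentrality 2.717; power 76.5%.

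| R2 (assumed) | 40/arm, k=4 | 40/arm, k=2 | 26/arm (assumed), k=4 |
|---|---|---|---|
| None added | 74.4% | 74.4% | 55.3% |
| 0% | 72.1% | 73.2% | 51.7% |
| 5% | 74.2% | 75.4% | 53.8% |
| 10% | 76.5% | 77.6% | 56.0% |
| 15% | 78.8% | 79.9% | 58.4% |
| 20% | 81.2% | 82.2% | 61.0% |

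Simulation with independent normal covariates (40,000 trials per cell) agrees to within about 1 point. Break-even R2 at 40 per arm is about 5.4% for four covariates and 2.7% for two. At 26 per arm it is about 8.5% for four.

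**4. Type I error**

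This used 20,000 simulated null trials per R2 value, 40 per arm, with four candidate covariates and R2 of 0, 10%, 20% and 30%.

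| Rule | Rejection rate |
|---|---|
| Fixed model, base or fully adjusted | 5.0-5.2% |
| Covariates added only for baseline imbalance (absolute t > 1.645), blind to outcome | 4.1-5.2% |
| Smaller p of base and fully adjusted models | 6.2%, 6.8%, 7.3%, 7.7% |
| Smallest p over all 16 covariate subsets | 7.2%, 9.0%, 10.6%, 12.8% |

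**The case against.** **The SAP already settles the model.** It supersedes the protocol, fixes one covariate set and contains no conditional clause. SAP 5.1 applies only before lock and only if assumptions fail, and the code stays closed until lock. This largely stands. A reader might infer that type I error is open at 7-13%, but that needs an unblinded search over 16 models, which the governing SAP does not allow. Even the protocol clause describes one adjusted analysis. What remains is an ambiguity: the clause was never withdrawn, although the protocol says the SAP will detail modifications, and SAP 5.1 lets a departure be explained in the CSR.

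**Adjustment is not free.** This stands. A reader might shrink the SD to 12.5 × √(1 − R2) and read off 77%, 79% and 81% at R2 of 5%, 10% and 15%. That ignores the cost of estimating four covariates. Once it is charged, nothing is gained at R2 of 5%, and power falls if the covariates are useless.

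**The list may not transfer.** AK002-016 enrolled EG and/or EoD. The documents report an influence on TSS change, not variance explained beyond baseline TSS and gender in an EoD-only, restricted population. Nor do they say whether the SD of 12.5 is already net of baseline. This also stands. It is a reason to check the AK002-016 data before choosing a set, and to keep the set short.

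**Conclusion.** The point holds as an inexpensive improvement. Four variables the sponsor called influential have no term in the primary TSS model, and an undefined adjustment clause remains in the protocol without being expressly withdrawn.

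Two limits apply. A reader might infer that leaving covariates out biases the treatment comparison; under randomization it does not, and the loss is one of precision. Type I error is at risk only if the clause is treated as live and applied using outcomes by arm: about 6-8% for the better of two models, with no inflation under an outcome-blind rule.

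The size of the power gain depends on an R2 the documents do not give. With four covariates at 40 per arm it runs from no gain at R2 of 5% to about 7 points at 20%. If they explain nothing, the loss is about 2-3 points at 40 per arm and 3-4 at an assumed 26 per arm. The 40 per arm counts all enrolled patients; the Evaluable number may be smaller, and no rate is stated.

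**What to change.** Before unblinding:

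1. In SAP 6.11.4 and its code, prespecify a short fixed set of the omitted baselines, or give the reason for leaving them out. Age and baseline duodenal eosinophil count are natural candidates, the latter because it is already in the imputation models. Add IBS history or diarrhea frequency only if AK002-016 shows that they explain variance beyond baseline TSS and gender. Choosing on AK002-016 data alone does not affect type I error in this trial.
2. Carry the same set into the sensitivity models in SAP 6.11.5 and the code in SAP Appendix 4.
3. State in the SAP that the conditional clause in Protocol 15.6.1 and the synopsis is withdrawn, or that any such analysis is supplementary and cannot replace the primary result.

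The cost is a few lines of text and code, with no new data and no patient burden. The statistical downside is one degree of freedom per covariate and a small power loss if the set proves uninformative: about 1 point for two covariates at 40 per arm.

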The pattern-mixture model will be implemented using multiple imputations, and the inference of this sensitivity analysis will be based on the combined estimates using the standard multiple imputation technique. The imputed data sets will be analyzed with the same MMRM model utilized in the primary analysis and then summarized using PROC MIANALZE. The other is to analyze the average of Week 23 through Week 24 using ANCOVA with treatment and study site (with pooling by geographic location) as factors, gender and baseline TSS (continuous) as covariates. Missing Week 23 through Week 24 weekly TSS will be imputed prior to ANCOVA using SAS PROC MI under the MAR assumption. Detailed specifications for the missing data imputation will be provided in the SAP.

Analysis of binary secondary endpoints will be based on the CMH test stratified by the randomization stratification factor (baseline TSS <28 vs \geq 28).

Change from baseline in continuous secondary outcomes measured at multiple post-baseline time points will be analyzed longitudinally using MMRM techniques. The model will include fixed effects for baseline value, treatment, week, treatment by week interaction, baseline value by week interaction, and allow for random subject effects. The model variance-covariance matrix will be unstructured. However, if computation does not converge, the matrix will take the form of Toeplitz, AR(1), and compound symmetry, whichever converges first. The Kenward-Rogers approach for computing denominator degrees of freedom will be used to account appropriately for pooling of within-subject and between-subject variance estimates. Least square means and the 95% CI for the between group difference will be estimated for each week.

To control for the overall false-positive error rate, the hypothesis testing for the primary and secondary endpoints using the Evaluable population in the subgroup defined above as the only population for primary inference are ordered as follows:

- The 2 co-primary efficacy endpoints will each be tested 2-sided at $\alpha=0.05$ level. If both tests are statistically significant, the hypothesis tests for the secondary endpoints will proceed sequentially based on the order specified in Section 4.2.

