### 3. Study Design

#### 3.1 General Description

This is a Phase 3, multicenter, randomized, double-blind, placebo-controlled study to evaluate the efficacy and safety of AK002 in subjects with moderately to severely active EoD without EG who have an inadequate response, lost response, or were intolerant to standard therapies.

Subjects enrolled in the study will receive 6 infusions of placebo or AK002 administered every 4 weeks and will be followed for 12 weeks after the last dose unless subjects elect to enter the optional long-term extension of the study.

Subjects who have signed the informed consent form (ICF) will be screened during 21-45 days prior to Study Day 1.

The study will be carried out as follows:

- A screening period of 21–45 days with baseline evaluations for study eligibility, including active symptoms of disease (gathered by the patient reported outcome [PRO] questionnaire completed during screening) and EGD and colonoscopy (performed on the same day) with biopsy.
- Stool antigen test for *Helicobacter pylori* (*H. pylori*) will be assessed during screening to confirm no active *H. pylori* infection exists. If *H. pylori* is detected in tissue biopsies by the central pathologist, the patient should be excluded from the trial.
- If subjects meet histology and symptom eligibility criteria, they will be randomized after being stratified by the highest weekly TSS of disease activity recorded during the screening period (<28 or ≥28 strata). The interactive response technology (IRT) will randomly assign subjects 1:1 to receive AK002 or placebo.
- Pre-study medications and dietary restrictions will remain unchanged throughout the study. Systemic or topical steroids above 10 mg prednisone will not be allowed except as a premedication prior to the first infusion only or due to unforeseen medical circumstances where it is deemed to be medically necessary to treat an unrelated medical condition or to treat an IRR that occurs during infusion.

- Eligible subjects will receive the first dose of placebo or AK002 (3 mg/kg) on Day 1 with premedication of 80 mg oral prednisone 12–24 hours prior to the start of the infusion.
- If the study drug is well tolerated (no stopping rules being met), subjects will receive additional doses of placebo or AK002 (3 mg/kg) on Days 29, 57, 85, 113, and 141. With the exception of Day 1, steroid premedication will only be allowed with the written approval of the Medical Monitor.

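### If the unstructured MMRM matrix fails, every named fallback assumes equal variance at all periods, so the Weeks 23–24 standard error can be off in either direction

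*SAP*

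**What the plan says.** The second co-primary endpoint is the change in TSS from baseline to Weeks 23–24, analysed by MMRM (SAP 6.11.4). The first choice of covariance is clear: "The model variance-covariance matrix will be unstructured". If that does not converge, "the matrix will take the form of Toeplitz, autoregressive, or compound symmetry, whichever converges first". Protocol 15.6.1 and the protocol synopsis give the same list. None of the three structures is described as heterogeneous.

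The sample code requests Kenward-Roger degrees of freedom ("TRTMT*AVISITN B_TTS*AVISITN / DDFM=KR") and no empirical (sandwich) option, so standard errors are model-based. The repeated factor is biweekly: "AVISITN = time point (i.e., Weeks 1-2, Weeks 3-4, ..., Weeks 23-24", which makes 12 periods. The ESTIMATE statement targets the last period alone. The same section has a separate simplification step: if the model does not converge with pooled site as a random effect, pooled site becomes a fixed effect.

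**The concern.** In their plain forms, Toeplitz, AR(1) and compound symmetry model how correlation depends on the gap between periods but give every period the same variance. The primary test uses one period, the last. If residual variance at Weeks 23–24 differs from the average over the 12 periods, the fallback puts the average in place of the value the test needs. Kenward-Roger adjusts for small-sample estimation of the covariance parameters; it does not correct a wrong covariance model.

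The fallback is not remote. An unstructured matrix has 12 × 13 / 2 = 78 parameters for biweekly periods, or 24 × 25 / 2 = 300 if the word week in the text is taken literally. These are estimated from about 80 patients less the Excluded population. The affected result is a co-primary p-value, and the histology co-primary gives little protection because its power exceeds 99% at the planned rates of 0.6 and 0.1.

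**Working it through.** **Inputs from the documents.** Two-sided alpha 0.05 (SAP 5.8), 1:1 allocation, 40 per arm, difference 7.4 and SD 12.5 (SAP 3.5: "A sample size of approximately 40 patients per treatment group will provide 80% power to detect a statistically significant difference of 7.4 points", "assuming a common standard deviation of 12.5 points"), and 12 biweekly periods (SAP 6.11.4). **Assumed:** every SD before Weeks 23–24, since none is given.

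**The plan's own figure.** SE of the difference = 12.5 × √(2/40) = 2.795. Then 7.4 / 2.795 = 2.648, and power = Φ(2.648 − 1.96) = 75.4%, not the stated 80%. That mismatch is a separate matter. I use 75.4% below only as the reference for lost power.

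**Closed form.** With complete data and covariate effects by period, the estimated difference at the last period does not depend on the covariance structure; only its standard error does. A common-variance model uses approximately the mean of the 12 period variances. So

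- r = √(mean of period variances / variance at Weeks 23–24)
- type I error = 2 × (1 − Φ(1.96 × r))

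Worked case, SD rising linearly from 10 to 12.5: mean variance 127.2; 127.2 / 156.25 = 0.814; r = 0.902; 1.96 × 0.902 = 1.768; type I error 7.7%.

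| SD at Weeks 1–2 → Weeks 23–24 (linear, assumed) | r | Type I error |
|---|---|---|
| 12.5 → 12.5 | 1.000 | 5.0% |
| 11 → 12.5 | 0.941 | 6.5% |
| 10 → 12.5 | 0.902 | 7.7% |
| 8 → 12.5 | 0.828 | 10.5% |
| 6.25 → 12.5 | 0.766 | 13.3% |
| 14 → 12.5 | 1.061 | 3.8% |
| 15 → 12.5 | 1.102 | 3.1% |

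For 14 → 12.5, power is roughly Φ(2.648 − 1.96 × 1.061) = 71.5%, against 75.4%.

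**Simulation check.** REML fits under the null used 40 per arm, 12 periods, complete data, no centre effect and an assumed correlation of 0.4 + 0.6 × 0.85^lag. There were 1,500–2,000 runs, or 600–800 for the heterogeneous forms.

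- Homogeneous fallbacks: 4.9–5.0% for constant SD; 7.5–7.7% for 10 → 12.5; 10.0–11.5% for 8 → 12.5; 13.2–13.8% for 6.25 → 12.5; 3.2–3.3% for 15 → 12.5.
- Early rise then plateau (correlation with baseline decaying from 0.9 to 0.5): 8.1–9.1%, against 7.6% from the closed form.
- Unstructured: 4.9–5.3%.
- Heterogeneous Toeplitz, AR(1) and compound symmetry: 4.5–6.3%, with a Monte Carlo standard error of 0.8–1.0 point.

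**What the documents suggest about direction.** SAP Table 7 gives standard errors of weekly mean TSS in Phase 2. With no days missing, the value is 3.092 at Week 1, 2.864 at Week 13 and 2.388 at Week 14. Assuming equal n per week, the mean of the 14 squared values is 8.946 and Week 14 squared is 5.703. The ratio is 1.569, r = 1.252 and type I error is 1.4%. Without Week 14 it is 9.196 / 8.202 = 1.121, r = 1.059 and 3.8%. Both are conservative.

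**The case against.** The strongest reply is that nothing in the documents shows rising variance, and the one relevant table points the other way. That stands. Table 7 does not settle the matter, though: it is raw TSS over 14 weeks, with no n per week and no adjustment for baseline. The MMRM adjusts for baseline by period. If baseline predicts early periods better than late ones, residual variance could rise even where raw variance does not. If the Table 7 pattern is combined with a baseline correlation decaying from 0.9 to 0.5, type I error is 2.7%, still conservative.

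Second, failure of the unstructured fit is not shown, and the plan already has a step that removes the random site effect. Both are fair. The probability of reaching the fallback is unknown.

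Third, the ANCOVA at Weeks 23–24 (SAP 6.11.5) does not pool variance over periods and would expose a distorted MMRM standard error. SAP 5.1 also allows other methods before database lock. Neither is a prespecified primary remedy: the ANCOVA is a sensitivity analysis, and the SAP 5.1 clause names no method.

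A reader might also infer that the plan sets no order among the fallbacks. A list followed by a first-to-converge rule reads naturally as trying the structures as listed, so I do not press that.

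**Conclusion.** The point holds conditionally. If the unstructured matrix fails and residual variance differs across periods, the Weeks 23–24 standard error is wrong. Type I error is about 6.5% to 13% for SD growth of about 1.1- to 2-fold. For SD falling from 14 to 12.5 it is about 3.8%, with some loss of power. These sizes rest on assumed SD paths, complete data and a final SD of 12.5.

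A stronger reading is tempting: that whenever unstructured fails, type I error rises well above 5%. The documents do not support it. With constant variance the fallback holds 5%; error of 10% or more needs fairly steady growth of about 1.5-fold; and the direction is unknown. This is an optional improvement to a contingency rule, not a defect in the main analysis.

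**What to change.** In SAP 6.11.4, replace the fallback list with heterogeneous structures tried in a stated order: TOEPH, then ARH(1), then CSH. Keep DDFM=KR and the existing step that moves pooled site to a fixed effect. The SAP supersedes the protocol on statistical methods, so the change can be made there. It protects the test in both directions.

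The cost is one sentence, the corresponding covariance type in the code, and about 11 extra variance parameters in the fallback (12 period variances instead of one). If a sandwich standard error is added as a last resort for a homogeneous structure, specify a small-sample-corrected version, because the uncorrected one can be anti-conservative at this sample size.

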## **5.7 Multicenter Study**

The study will have approximately 35 sites. Analysis of site effect will be based on analysis centers. Analysis centers will be formed in such a way that there are sufficient subjects per

pooled analysis center for the assessment of study site effects. Pooling of study sites by geographic location is described below:

- **Analysis Center 1:** Massachusetts, Connecticut, Rhode Island, New York, New Jersey, Pennsylvania, District of Columbia, Maryland, Maine, Vermont, Delaware, and New Hampshire
- **Analysis Center 2:** Virginia, West Virginia, South Carolina, Georgia, Mississippi, Florida, Alabama, Louisiana
- **Analysis Center 3:** North Carolina, Tennessee, Ohio, Michigan, Indiana, Kentucky
- **Analysis Center 4:** South Dakota, Arkansas, Minnesota, Wisconsin, North Dakota, Illinois, Missouri, Iowa, Texas, Oklahoma, Kansas, Nebraska, Wyoming, Colorado
- **Analysis Center 5:** Utah, New Mexico, Arizona, California, Oregon, Washington, Idaho, Hawaii, Alaska, Montana, Nevada

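### The sample SAS code for the symptom co-primary enters analysis centre as both fixed and random, so it matches neither the stated primary model nor the stated fallback

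*SAP*

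**What the plan says.** The prose of SAP 6.11.4 is clear. The MMRM has "study site (with pooling by geographic location) as random effect", and the alternative is conditional: "If the model does not converge with pooled sites as a random effect, it will be simplified with pooled site as a fixed effect". Protocol 15.6.1 gives the same primary model and the same fallback. SAP 5.7 pools the sites into five analysis centres.

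The code that follows is introduced with "A sample of the SAS code for MMRM analysis is provided as below". It calls "proc mixed data=tss method=reml", declares centre as categorical ("class TRTMT USUBJID AVISITN ANALYSIS_CENTER GENDER"), lists centre among the fixed effects ("model CHG= B_TSS TRTMT AVISITN ANALYSIS_CENTER GENDER"), and then adds "RANDOM ANALYSIS_CENTER". The same `MODEL` and `RANDOM` statements appear in Step 3 of the placebo-based pattern-mixture analysis in SAP 6.11.5.

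SAP 4.2.6 names the LS mean and standard error for the Weeks 23–24 change, along with the between-treatment difference, as the summary measure of the estimand for this endpoint.

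**The concern.** No sentence in either document describes a model with centre in both places. The ANCOVA code in SAP 6.11.5 and Appendix 4 has centre fixed with no `RANDOM` statement, so the duplication is not a convention of this SAP.

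This is the model for the symptom co-primary, and secondary testing opens only if both co-primaries succeed (SAP 5.8). A programmer who starts from the sample would not obtain the random-site fit that the prose puts first. The fixed-site result would arrive without the non-convergence that is supposed to trigger it. The per-arm standard errors would also take in a centre variance for which the data provide no estimate.

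**Working it through.** The plan attaches no figure to this model, so there is none to reproduce. The check sets text against code, then follows the algebra, then illustrates it.

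**1. Text against code**

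| Source | Centre in `MODEL` | Centre in `RANDOM` |
|---|---|---|
| Primary model, prose of SAP 6.11.4 and Protocol 15.6.1 | no | yes |
| Fallback, same sections | yes | no |
| Code in SAP 6.11.4 and 6.11.5 Step 3 | yes | yes |
| ANCOVA code, SAP 6.11.5 and Appendix 4 | yes | no |

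**2. Identifiability.** Write V = R + σ²ZZ′, where Z holds the centre indicators and σ² is the centre variance. REML uses only contrasts K′y with K′X = 0, and Var(K′y) = K′RK + σ²K′ZZ′K. If centre is a categorical fixed effect, Z = XA for some matrix A. Then K′Z = K′XA = 0 and σ² drops out of the likelihood. This holds for any data.

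**3. Illustration.** Inputs from the documents: 80 subjects, 1:1 allocation, SD 12.5, five centres, 12 biweekly periods. Assumptions: one simulated data set; R treated as known, with within-patient correlation 0.5 + 0.5 × 0.6^lag; centre effects with SD 3; baseline TSS with mean 28 and SD 9.

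Fixed-effect columns without centre: 12 period + 12 treatment-by-period + 12 baseline-by-period + 1 gender = 37. Adding centre gives 37 + 4 = 41.

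- Printed code: rank X = 41 and rank [X Z] = 41, so Z adds nothing.
- Centre in `RANDOM` only: rank X = 37 and rank [X Z] = 41, so Z adds four dimensions.

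| σ² | Both: log-likelihood | Both: difference (SE) | Random only: log-likelihood | Random only: difference (SE) |
|---|---|---|---|---|
| 0 | −2441.288111 | −8.404 (2.823) | −2446.99 | −8.822 (2.805) |
| 9 | −2441.288111 | −8.404 (2.823) | −2448.01 | −8.559 (2.816) |
| 100 | −2441.288111 | −8.404 (2.823) | −2451.49 | −8.425 (2.822) |
| 1000 | −2441.288111 | −8.404 (2.823) | −2455.93 | −8.406 (2.823) |

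With both terms, the row at σ² = 0 is the fixed-site model, and every other row equals it. In these data the largest gap from the random-only model is 8.822 − 8.404 = 0.418 points, or 0.418/2.823 = 0.15 of a standard error.

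**4. Per-arm LS means.** An LS mean averages the five centres equally, so a centre variance adds σ²/5 to its variance: SE = √(SE₀² + σ²/5). In a smaller illustration (70 patients, five centres, three periods, SD 12.5, assumed within-patient correlation 0.6), SE₀ = 2.11. A hypothetical σ² of 50 gives √(2.11² + 50/5) = √(4.45 + 10) = 3.80. The standard error of the difference stays at 2.99, because the centre term cancels between arms.

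**5. Other faults in the same blocks.**
- The interaction is written with `B_TTS`; the main effect in the same statement is `B_TSS`. `B_TTS` is defined nowhere.
- Two arms by 12 periods needs 2 × 12 = 24 interaction coefficients in `ESTIMATE`. Those printed are 10 zeros, −1, 11 zeros and 1, which is 10 + 1 + 11 + 1 = 23. Read in order, −1 is 11th and +1 is 23rd (12 + 11), which is the eleventh period of each arm, not the twelfth. This count should be checked against the source file.
- Step 3 of 6.11.5 reads `data=tss`, not the imputed output of Step 2, and has no `BY _imputation_`.

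**The case against.** The strongest reply is that this is labelled sample code beside clear prose, and an analysis programmed from the prose fits the right model. SAP 7 also requires a second programmer to reproduce the tables. `B_TTS` should stop the block at its first run, so someone would have to look at it. Once it runs, the difference and its standard error are exactly those of the prespecified fallback.

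Most of that stands, and it rules out three stronger readings that a reader might draw:

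- *The stated model will never be fitted.* This is true of the printed code. The documents do not support it for an analysis written from the text.
- *The confirmatory test is biased or loses control of type I error.* Nothing here shows that. The contrast is a legitimate, prespecified one.
- *The duplication will cause a convergence or Kenward-Roger failure and force the fallback, or a simpler covariance structure.* The information on σ² is zero, so trouble is possible, but no SAS run was made and the software may simply return zero for the variance.

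The per-arm range of 2.11 to 3.80 likewise comes from assumed variances, not from any value the documents or SAS would supply.

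Double programming does not dispose of the point. Two programmers who start from the same sample can agree with each other and still differ from the prose.

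**Conclusion.** The point holds as a contradiction between code and text in two places. The printed model is neither the primary nor the fallback, and under REML its centre variance is not identifiable; that part is algebra and rests on no assumption about the data. The effect on the treatment comparison is to substitute the fixed-site result, which in one simulated data set with known R differed from the random-site result by at most 0.15 of a standard error. The consequences that remain are the bypassed trigger and per-arm standard errors that would depend on whatever value the software assigns to the variance. How SAS would report this is untested. It should be corrected before programming, but it is not a flaw in the specified analysis itself.

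**What to change.** In SAP 6.11.4 and in 6.11.5 Step 3:

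- Primary block: remove `ANALYSIS_CENTER` from `MODEL` and keep "RANDOM ANALYSIS_CENTER".
- Fallback block, printed separately: keep `ANALYSIS_CENTER` in `MODEL` and omit the `RANDOM` statement.
- Replace `B_TTS` with `B_TSS`.

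While these blocks are open, confirm that `ESTIMATE` carries all 24 treatment-by-period coefficients with the non-zero ones on Weeks 23–24, and make Step 3 read the imputed data set by `_imputation_`.

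The cost is an edit to sample code in the SAP. The endpoint, the stated model, the sample size and the data collection do not change.
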